### 8.10. Other planned analyses

#### 8.10.1. Quality of life

Disease-specific quality-of-life measures (FDI, FaCE scale and SAQ) will be considered as continuous variables (composite scores 0-100). Depending of the distribution, appropriate statistical method (parametric/non-parametric) will be used to compare quality-of-life between groups at 1 and 12 months follow-up visits.

## 9. Determination of sample size

Sample size for the FACE study is calculated on the primary outcome (i.e. number (%)) of patients with total recover of the facial nerve palsy in each intervention group, measured by House-Brackmann grade 1, at 12 months follow-up). An 10% difference of the total recovery rate between groups (80% in placebo group versus 90% in prednisolone group) is an estimation from earlier non-RCT studies, interviews with children/parents (unpublished data) and a test of two independent proportions for estimation of the minimal relevant clinical improvement (MRC). To show that such a difference is significant ( $p < 0.05$ , two-sided test) with 80 % power, a total of 430 patients are needed. However, due to the uncertainty in the assumptions and to that a portion (10%) of patients not taking part of the study follow-up, 500 patients will be included in the FACE study (250 in each group).

## 10. Interim Analysis Plan

There will be no interim analysis in this study.

## 11. Changes in the Planned Analysis

Not applicable

## 12. Description of Derived Variables

Duration of AE: stop date minus onset date expressed in days

Variable	Algorithm in words	SAS Variable name
Complete recovery of palsy at month 1 according to SB scale	Healed (1) if sunnybrook scale at month 1 is 100. If sunnybrook at month 1 $\leq$ 99 then patients are considered as not healed (0)	Month1_SB_healed
Complete recovery of palsy at month 12 according to SB scale	Healed (1) if sunnybrook scale at Month 12 visit is 100. If sunnybrook at Month 12 visit $\leq$ 99 then patients are considered as not healed (0)	Month12_SB_ghealed
Complete recovery of palsy at month 1 according to HB scale	Healed (1) if HB scale at Month 1 visit =1. If HB scale at Month 1 visit >1 then patients are considered as not healed (0)	Month1_HB_healed
Complete recovery of palsy at month 12 according to HB scale	Healed (1) if HB scale at Month 12 visit =1. If HB scale at Month 12 visit >1 then patients are considered as not healed (0)	Month12_HB_healed
Compliance (%)	Compliance in % = (total number of capsules (10) minus Number of capsules remaining) * 100/10 (0% - 100%)	Compliance_pct

FaCE scale (Total score will be used)

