9.4 SUBJECT LOG AND SCREENING OF SUBJECTS

Participants will receive a consecutive screening number when signing the informed consent and are thereafter considered to be enrolled in the study.

It is the responsibility of the Investigator that all participants that have signed Informed Consent are listed on the "Screening and enrolment log". The reason for rejecting a participants before first treatment should be specified in the comment field of the log.

If the participant is eligible, he/she will receive a randomization number and the study drug bottle with the same randomization number will be distributed to the patient and the parents/guardians. It is the responsibility of the investigator to keep a patient identification log, identifying the individual behind each randomization number.

The Subject Enrolment and Identification log contains information to enable identification of each participant. It is included in the Investigator's File and shall be kept by the Principal Investigator in a safe place.

The participants will have the same randomization number through the study and this number will not be reused in case the participant is withdrawn from the study.

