10.2 DESCRIPTION OF INVESTIGATIONAL PRODUCTS

Capsule Prednisolon 5 mg (APL), dosage 1 mg/kg (max 50 mg) once daily for 10 days according to pre-calculated weight table (Table 2). All bottles include 100 capsules.

Capsule Placebo (APL), dosage once daily equivalent to 1 mg/kg (max 10 capsules) for 10 days according to pre-calculated weight table (Table 2). All bottles include 100 capsules.

See separate product information and pharmacological documents from APL for prednisolone and placebo.

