10.8 ACCOUNTABILITY OF INVESTIGATIONAL PRODUCTS

Accountability will be measured by counting remaining capsules in the bottles, which should be returned to the study nurse at the pediatric clinic after usage, at the latest at the 1 month follow-up visit.

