### 8.3. Treatment Administration/Compliance

The intervention is treatment with either prednisolone (capsule Prednisolone 5 mg), 1 mg/kg once daily in 10 days or control treatment (capsule placebo) once daily in 10 days. The number of capsules is based on the child's weight and presented in the table below:

Child's weight /kg	Number of capsules/day	Total number of capsules
5 - 9.9	2	20
10 - 14.9	3	30
15 - 19.9	4	40
20 - 24.9	5	50
25 - 29.9	6	60
30 - 34.9	7	70
35 - 39.9	8	80
40 - 44.9	9	90
>45	10	100

Capsule Prednisolon 5 mg (APL), dosage 1 mg/kg (max 50 mg) once daily for 10 days according to pre-calculated weight. All bottles include 100 capsules.

Compliance for the 10 day period:

Compliance (0-100%) = (Number of tablets actually taken x 100)/total number of capsules

Patients with treatment compliance less than 70% will be excluded from the PP analysis. Patients with 0% compliance will be excluded from ITT analysis.

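### SAP Section 12 computes compliance from a fixed total of 10 capsules, which fits no weight band and contradicts Section 8.3, although compliance decides PP and ITT exclusions

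*SAP*

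**What the plan says.** The SAP defines compliance twice.

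- Section 8.3 gives "Compliance (0-100%) = (Number of tablets actually taken x 100)/total number of capsules", introduced as "Compliance for the 10 day period". The dosing table just above has a column headed "Total number of capsules", running from 20 to 100 over nine weight bands. Table 2 in protocol Section 10.1 has the same totals.
- Section 12, which assigns the variable name Compliance_pct, gives "Compliance in % = (total number of capsules (10) minus Number of capsules remaining) * 100/10", with a stated range of 0 to 100%.

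Section 8.3 then uses compliance to define the analysis sets: "Patients with treatment compliance less than 70% will be excluded from the PP analysis. Patients with 0% compliance will be excluded from ITT analysis". Under SAP Section 7 the ITT set serves both efficacy and safety, and the PP set serves the primary endpoint only.

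The protocol fixes what the count will be. In Section 9.4, "the study drug bottle with the same randomization number will be distributed to the patient"; in Section 10.2, "All bottles include 100 capsules"; and in Section 10.8, "Accountability will be measured by counting remaining capsules in the bottles".

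**The concern.** Section 12 sets the course at 10 capsules for every child, but the smallest course in the dosing table is 20. In the dosing scheme, ten is only the number of treatment days and the daily capsule count in the heaviest band. Subtracting a capsule count from 10 therefore gives a score that depends on body weight as well as on adherence.

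This score selects patients. If Section 12 is programmed as written, children with the same adherence are kept in or dropped from the PP set according to weight, and some adherent children take the value that Section 8.3 uses to remove them from ITT. A child who took nothing would not score 0%, so the ITT rule would miss the case it was written for.

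**Working it through.** **Inputs.** Let d be capsules per day, 2 to 10 over the nine bands (SAP 8.3; protocol Table 2). The prescribed total is T = 10d. The bottle holds 100 (protocol 10.2). The limits are below 70% for PP and 0% for ITT (SAP 8.3).

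**Section 8.3, with T as the total.** Full adherence gives 10d x 100/10d = 100% in every band; one missed day gives 9d x 100/10d = 90%.

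**Section 12, reading A: remaining = capsules left in the bottle.** Full adherence leaves 100 - 10d, so the score is (10 - (100 - 10d)) x 100/10 = 100d - 900.

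**Section 12, reading B: remaining = prescribed capsules not taken.** One missed day leaves d, so the score is (10 - d) x 10. The score reaches 0% when 10 capsules are not taken, a true adherence of (10d - 10)/10d.

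| Weight (kg) | d | T | A: full adherence | B: one missed day (true 90%) | B: true adherence at which score is 0% |
|---|---|---|---|---|---|
| 5-9.9 | 2 | 20 | -700% | 80% | 50% |
| 10-14.9 | 3 | 30 | -600% | 70% | 67% |
| 15-19.9 | 4 | 40 | -500% | 60% | 75% |
| 20-24.9 | 5 | 50 | -400% | 50% | 80% |
| 25-29.9 | 6 | 60 | -300% | 40% | 83% |
| 30-34.9 | 7 | 70 | -200% | 30% | 86% |
| 35-39.9 | 8 | 80 | -100% | 20% | 88% |
| 40-44.9 | 9 | 90 | 0% | 10% | 89% |
| >45 | 10 | 100 | 100% | 0% | 90% |

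Under A, seven bands fall outside the stated range and eight fall below 70% at full adherence. Under B, full adherence scores 100% everywhere, but after one missed day seven bands fall below 70%.

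**The 70% rule as a limit on capsules returned.**

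- Section 8.3 needs at least 7d taken, so returned may be at most 100 - 7d: 86, 79, 72, 65, 58, 51, 44, 37 and 30 across the bands.
- Section 12 under A needs (10 - remaining) x 10 >= 70, so at most 3 may be returned in every band.

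**A child who took nothing.** Under A the score is (10 - 100) x 10 = -900%. Under B it is (10 - 10d) x 10, from -100% to -900%. Neither is 0%.

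**Reading C: 10 = treatment days, remaining = daily doses missed.** One missed day gives (10 - 1) x 100/10 = 90% in every band, equal to Section 8.3. Only this reading reconciles the two sections, but Section 12 says capsules for both quantities.

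**The case against.** The best defence is that this is a mislabelled unit. Reading C is probably what was intended: Section 8.3 refers to a 10-day period, and the 0 to 100% range fits. A workable formula stands beside the exclusion rules themselves. Section 7 defines ITT by receipt of at least one dose and available data, so dropping an adherent child on a false 0% would contradict Section 7 as well as Section 8.3. Scores of -100% to -700% would be noticed, and correcting the formula for those bands would correct it for all. The PP set has limited use, and the SAP still needs approval by a biostatistician not otherwise involved.

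Much of this stands. Harm requires that Section 12 is programmed literally, and large negative values would probably expose the error. Three things remain:

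- Section 12 is where the variable is specified, and the SAP does not say that Section 8.3 prevails.
- Not every wrong value is conspicuous. The 0% at 40-44.9 kg under A, and all the one-missed-day scores under B, lie inside the stated range. If a programmer truncated to that range (an assumption, not something the SAP says), the seven negative bands under A would also become 0%.
- Section 7 does not neutralise the 0% rule in Section 8.3. If Compliance_pct feeds that rule, the two sections would conflict for adherent children, with nothing to decide between them.

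The case report form fields and output shells were not available, so how the remaining count is recorded is unknown.

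**Conclusion.** The Section 12 formula is wrong as written and contradicts Section 8.3. The size of the error depends on what remaining means and on which section is programmed. With the bottle count that the protocol describes, fully adherent children in eight of nine bands fail the PP limit, and one band scores the ITT exclusion value. With prescribed capsules not taken, a single missed day fails the PP limit in seven bands and scores 0% in the heaviest. With Section 8.3 and the prescribed total, or with the days reading, there is no error.

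These results assume one 100-capsule bottle per child and complete return of unused capsules. The number of children affected cannot be given, because the documents contain no weight distribution. The point should be fixed before the SAP is final, since it settles who belongs to the analysis sets and costs little.

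**What to change.** Replace the Section 12 row with:

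Compliance_pct = 100 x (100 - capsules returned) / prescribed 10-day total for that child,

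where the denominator is 20, 30, ..., 100, taken from the total column in Section 8.3 or from the dosage noted in the CRF. With k missed days, returned = 100 - (10 - k)d, so the score is 100 x (10 - k)d/10d = 10 x (10 - k). For k = 0, 1, 3 and 4 this is 100, 90, 70 and 60% in all nine bands, and nothing taken gives 0%.

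In Section 8.3:

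- use the same formula and name the prescribed total explicitly, because that section also mentions the bottle content of 100;
- state that Compliance_pct is the variable behind the 70% and 0% rules;
- say that values above 100% (more capsules gone than prescribed) trigger neither rule, are queried and are reported as computed, and adjust the stated range;
- treat an unreturned bottle as missing, not as zero returned. Entered as zero, it would score 100 x 100/20 = 500% in the lightest band. Say how a child with missing compliance is classified.

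The cost is SAP wording in two places and the matching derivation code. Both inputs are already planned, and no protocol text changes. Whether the output shells in Appendix 1 need an edit is not known.

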## APPENDIX B

Facial Movement Score	= (((Items 1 + 2 + 3) - # valid) / 4 $\times$ (# valid)) $\times$ 100
Facial Comfort Score	= (((Items 4 + 6 + 16) - # valid) / 4 $\times$ (# valid)) $\times$ 100
Oral Function Score	= (((Items 11 + 12) - # valid) / 4 $\times$ (# valid)) $\times$ 100
Eye Comfort Score	= (((Items 5 + 7) - # valid) / 4 $\times$ (# valid)) $\times$ 100
Lacrimal Control Score	= (((Item 8) - # valid) / 4 $\times$ (# valid)) $\times$ 100
Social Function Score	= (((Items 9 + 10 + 14 + 15) - # valid) / 4 $\times$ (# valid)) $\times$ 100
Total Score	= (((Sum of all 15 items) - # valid) / 4 $\times$ (# valid)) $\times$ 100

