#### 5.2.4. Secondary outcome measures

The physician performed Sunnybrook grading scale (100 is normal and 0 is total loss of function) is chosen as secondary outcome measure as it correlates well to the House-Brackmann scale in adult patients, is easy to perform and evaluates facial function in rest and activity. Both the House-Brackmann and the Sunnybrook grading scale are included in order to be able to evaluate agreement between them, and to decide which one has the best most preferable utility and thus should be recommended for evaluation of facial nerve palsy in children. Sunnybrook has also been used for prediction of prognosis in adult patients and will now be evaluated for prediction of recovery in pediatric patients.

Three validated child/parent assessed instruments for disease specific quality-of-life are chosen as additional secondary outcome measures for patient/parent reported outcome measures (PROMs), in order to examine and better understand facial disability (18-21).

The Facial disability index (FDI) consists of 10 different items (6 is full satisfaction, 1 is no satisfaction) divided into two domains; physical function (with composite score of -25 – 100) and social/well-being function (with a composite score of 0-100) (18).

The Facial Clinimetric Evaluation Scale (FaCE scale) includes 15 items (5 is full satisfaction, 1 is no satisfaction) in six domains and a total composite score of 0-100.

The Synkinesis Assessment Questionnaire (SAQ) includes 9 items concerning defect recovery (1 is full satisfaction, 5 is no satisfaction) and gives composite score of 0-100.

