### 8.6.2. Correlation and agreement

For correlations between degree of recovery measured by physician assessed grading (House-Brackmann or Sunnybrook) and child/parent assessed quality-of-life measures at 1 and 12 months follow-up visits, Spearman's correlation will be used.

QoL will be measured with:

- Facial Clinimetric Evaluation (FaCE) scale (0-100)
- Facial Disability Index (FDI) scale, as two separate subscales Physical function (0-100) and Social/Wellbeing (0-100).
- Synkinesis Assessment Questionnaire (SAQ) scale (0-100)

Agreement between House-Brackmann and Sunnybrook grading scale will be assessed using Cohen's kappa.

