# valid = number of items within the domain for which an adequate response was given.

SAQ Total Synkinesis Score: (Sum of Scores 1 to 9)/45 x 100

FDI Will be used as subscale Physical and social/well-being function

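### The FaCE scoring lines in SAP section 12 lack a bracket around the denominator: evaluated as written, the Total Score reaches 22,500 instead of 100

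*SAP*

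**What the plan says.** Both documents list the FaCE scale at 1 and 12 months among the secondary endpoints (protocol 7.2, SAP 5.2.3). SAP section 12 names the version to be analysed: "FaCE scale (Total score will be used".

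The scoring block in section 12, headed Appendix B, has seven lines of the same form. The Total Score line begins "Sum of all 15 items) - # valid) / 4", continues with a multiplication by (# valid), closes the bracket and multiplies by 100. The six domain lines follow the same pattern, for example "Items 1 + 2 + 3) - # valid) / 4" for facial movement and "Items 4 + 6 + 16) - # valid) / 4" for facial comfort. The term # valid is the "number of items within the domain for which an adequate response was given".

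The SAP gives the intended range three times. In section 5.2.4 the scale "includes 15 items (5 is full satisfaction, 1 is no satisfaction) in six domains and a total composite score of 0-100". Section 8.6.2 lists the "Facial Clinimetric Evaluation (FaCE) scale (0-100". Section 8.10.1 says that the three quality-of-life measures "will be considered as continuous variables (composite scores 0-100".

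**The concern.** Section 12 is the specification from which the analysis variables are programmed. SAS, R and SPSS, the packages named in SAP section 14, give division and multiplication equal precedence and work from left to right. Typed as printed, the line divides by 4 and then multiplies by the number of valid items, when it should divide by both. The result does not fit the 0-100 range.

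The score is used in two analyses: the comparison between arms at 1 and 12 months (section 8.10.1) and the Spearman correlations with the House-Brackmann and Sunnybrook gradings (section 8.6.2). A wrong but constant scale would spoil only the reported values. A factor that depends on how many items were answered could also change the ordering of patients, and so affect both analyses.

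**Working it through.** Inputs:

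- 15 items, each scored 1 to 5, with an intended total of 0-100 (SAP 5.2.4).
- v = number of items validly answered (SAP 12).
- S = sum of the answered items, so S runs from v to 5v.

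**Reading A, with 4 × v as the whole denominator:** A = 100 × (S − v) / (4 × v).

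- v = 15, S = 15: 100 × 0 / 60 = 0.
- v = 15, S = 75: 100 × 60 / 60 = 100.
- For any v, the maximum is 100 × (5v − v) / (4v) = 100.

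This reproduces the SAP's stated range, whatever the number of valid items, for the total and for every domain.

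**Reading B, the printed line under standard precedence:** B = ((S − v) / 4) × v × 100.

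- v = 15, S = 75: (60 / 4) × 15 × 100 = 22,500.
- v = 14, S = 70: (56 / 4) × 14 × 100 = 19,600.
- v = 10, S = 50: (40 / 4) × 10 × 100 = 10,000.

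By the same formula, the maxima of complete domains are 900 for the two three-item domains, 400 for the two two-item domains, 100 for the single-item domain and 1,600 for the four-item domain.

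**Relation between the two.** B / A = [(S − v) × v × 100 / 4] / [100 × (S − v) / (4v)] = v². With every form complete, the factor is 15² = 225 throughout. Ranks are then unchanged, and so are the p-values of rank tests, t-tests and Spearman correlations. Reported means, medians and differences would be 225 times too large.

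**Incomplete forms.** The factor drops to 14² = 196 with one blank item and 10² = 100 with five.

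- A child with 15 items at mean 3: S = 45, A = 100 × 30 / 60 = 50, B = (30 / 4) × 15 × 100 = 11,250.
- A child with 10 items at mean 4: S = 40, A = 100 × 30 / 40 = 75, B = (30 / 4) × 10 × 100 = 7,500.

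The second child does better on the intended score and worse on the printed one. A single blank also matters: a perfect form with 14 valid items gives 19,600, level with a complete form whose intended score is 19,600 / 225 = 87.1.

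**Item count.** The domain lines use 1, 2, 3; 4, 6, 16; 11, 12; 5, 7; 8; and 9, 10, 14, 15. That is 3 + 3 + 2 + 2 + 1 + 4 = 15 distinct items in six domains, which agrees with section 5.2.4.

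**The case against.** The strongest reply is that this is notation. If 4 × (# valid) is taken as one denominator, the formula is exactly right, and the SAP's stated range admits no other reading. Section 8 requires minimum and maximum values for quantitative variables, so a FaCE maximum in the thousands would show in the first table. The layout may also be at fault: a stacked fraction could have been flattened in the PDF text. The FDI formulas in the same section keep their fraction form while all seven FaCE lines carry an inline slash, so this is unproven either way.

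Most of this stands. It shows that the intended score can be recovered and that the error would probably be caught. It does not make the written rule correct, and a derivation rule should not rely on the programmer to repair it. Nor do the stated ranges in this SAP always match their formulas. The SAQ is described as 9 items scored 1 to 5 with a 0-100 composite, yet its formula in section 12 cannot fall below 9 / 45 × 100 = 20.

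A reader might also infer that the item list is wrong, because it skips 13 and includes 16 for a 15-item scale. The documents do not support that. The list holds exactly 15 distinct items, and the total can be read as the sum of those 15. A form numbered to 16 with one unscored question would fit. The questionnaire form is not in the documents, and nothing in the SAP tells the programmer to sum questions 1 to 15.

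**Conclusion.** The point holds as a minor correction to a secondary endpoint. Evaluated as written, the FaCE Total Score equals the intended score times v², with a maximum of 22,500 on complete forms, which contradicts the SAP's own 0-100 range.

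The practical damage is limited. With complete forms only the reported scale is wrong. The ordering of patients is distorted only if partly completed forms are scored. The # valid term implies that they are, although section 8.8 prescribes complete-case analysis for secondary endpoints without saying whether that excludes a form with blank items. The documents give neither a rate of incomplete forms nor a minimum number of answered items, so the size of any effect on the comparison between arms cannot be stated; the 10-item example is illustrative.

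A reader might go further and conclude that the endpoint will be mis-scored. That would require the stated range and the minimum-maximum tables to be ignored. The primary endpoint, the sample size and the safety analyses are not touched.

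**What to change.** In SAP section 12, write Total = 100 × (sum of answered items − v) / (4 × v), with v the number of valid items, and put the same bracket around the denominator in the six domain lines. Add a programmed check that every derived FaCE score lies between 0 and 100. While the section is open, confirm that the numbering on the questionnaire form matches the 15 items listed (1-12, 14, 15 and 16).

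The cost is seven edited lines, one range check and one look at the form. Nothing in the design, data collection or other analyses changes.

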# valid = number of items within the domain for which an adequate response was given.

SAQ Total Synkinesis Score: (Sum of Scores 1 to 9)/45 x 100

FDI Will be used as subscale Physical and social/well-being function

